6.2.1.6 Dosage Limiting Toxicities

The grading of adverse events will be based on the guidelines provided in the Common Terminology Criteria for Adverse Events (CTCAE) version 4.0 (available online at <http://evs.nci.nih.gov/ftp1/CTCAE/About.html>). Determination of the severity of adverse events will be consistent with Common Terminology Criteria for Adverse Events (CTCAE) version 4.0. The relationship of an adverse event to investigational product will be determined by the Investigator. An event should be considered related to treatment if, in the Investigator's medical judgment, there is a reasonable possibility that the event may have been caused by AMG 224.

A DLT is defined as a Grade 3 or higher non-hematological or a Grade 4 hematologic adverse event that occurs during the DLT window (day 1 through day 28 after the administration of the first dose of AMG 224) in Part 1 Dose Exploration unless clearly attributable to causes other than AMG 224 treatment. DLT toxicities do not include fatigue, nausea, diarrhea, vomiting, neutropenia, anemia, thrombocytopenia and lymphopenia, increased serum creatinine or electrolytes abnormalities that are not clinically significant and require no treatment unless the following criteria are met:

Hematological toxicity:

- Grade 4 neutropenia lasting > 7 days
- Grade 3 or 4 neutropenia with fever > 38.5°C
- Grade 3 thrombocytopenia with ≥ Grade 2 hemorrhage
- Grade 4 thrombocytopenia lasting > 7 days
- Grade 3 anemia with symptoms or required intervention (eg, transfusion)
- Grade 4 anemia
- Lymphopenia of any grade is not considered a DLT

Approved

Non-hematological toxicity:

- \geq Grade 3 nausea, vomiting or diarrhea persisting more than 3 days despite optimal medical support
- Grade 3 fatigue persisting > 7 days
- \geq Grade 3 acute kidney injury (creatinine >3 X baseline or > 4.0 mg/dL) lasting > 3 days
- Elevation of either AST or ALT according to the following criteria:
 - $> 8x$ ULN;
 - $> 5x$ ULN but $< 8x$ ULN for ≥ 2 weeks;
 - $> 5x$ ULN but $< 8x$ ULN and unable to adhere to enhanced monitoring schedule; or
 - $> 3x$ ULN with clinical signs or symptoms that is consistent with hepatitis (such as right upper quadrant pain/tenderness, fever, nausea, vomiting, jaundice, rash or eosinophilia ($> 5\%$)).
- TBIL $> 3x$ ULN

Any subject meeting the criteria for Hy's Law case (ie, severe drug-induced liver injury) will be considered a DLT. A Hy's Law case is defined as: AST or ALT values of $\geq 3x$ ULN AND with serum total bilirubin level (TBL) of $> 2x$ ULN without signs of cholestasis and with no other clear alternative reason to explain the observed liver-related laboratory abnormalities (see [Section 6.4](#) for hepatotoxicity management and [Appendix A](#) for further explanation of Hy's law case and Management of Hepatic Function).

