3. EXPERIMENTAL PLAN

3.1 Study Design

This is a Phase 1, first-in-human, multicenter; non-randomized, open-label, dose-exploration and dose expansion study of AMG 224 IV Q3W for subjects with relapsed or refractory multiple myeloma. The study will be conducted in two parts: Part 1 - Dose Exploration and Part 2 - Dose Expansion.

Eligible subjects enrolled in the study will receive AMG 224 IV once Q3W beginning at study Day 1. During the initial DLT window (Day 1 through Day 28) subjects will be assessed for DLT. DLTs are defined in [Section 6.2.1.6](#). Dosing with AMG 224 may continue Q3W unless there is evidence of progressive disease (PD) defined by IMWG, the subject becomes intolerant to the study medication, signs and symptoms of clinical progression are evident as determined by the principal investigator, or the subject withdraws consent.

Part 1 – Dose Exploration

In Part 1 for the first dose level and at each new higher dose level, the first enrolled subject will be treated, and then after a period of 24 hours, subsequent subjects will be treated, provided that there are no safety concerns relating to the treatment of the first subject.

The dose-exploration cohorts will define the preliminary MTD, safety, tolerability, PK, and PD of AMG 224. A 3+3 design will be used to make a preliminary estimate of MTD. The preliminary MTD is defined as the maximum dose at which fewer than 33% of subjects experience a DLT. A final estimate of the MTD will be made using data from Dose Exploration and Dose Expansion. Planned dose levels for the dose-exploration cohorts are as follows: 30, [REDACTED] of AMG 224 (IV; Q3W).

Approved

Dose exploration decisions will be made by the Dose Level Review Team (DLRT). All cumulative safety and laboratory data will be reviewed prior to making dose exploration decisions. Safety data from all enrolled subjects in preceding cohorts and dose levels will also be considered. Additionally, the DLRT may stop enrollment into a cohort at any time to evaluate safety.

3+3 Design:

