10.3.1 Interim Analyses

Safety data will be reviewed on an ongoing basis. The Dose Level Review Team (DLRT, see [Section 10.3.2](#)) will review all available cumulative data by cohort prior to making dose escalation decisions. Adverse events and DLTs observed in all subjects will be evaluated continually and considered in all enrollment and dosing decisions.

During dose-expansion, the DLRT will review safety after 5 subjects have enrolled (combining Group A and Group B subjects) and completed 28 days on study. A TPI Bayesian model (see [Section 10.4.2.3](#)) utilizing all current DLT-evaluable subjects will be

Approved

fit to evaluate the appropriateness of the preliminary MTD from dose exploration. The subsequent subjects to be enrolled in dose expansion may be dosed with the updated dose level, determined by the DLRT.

10.3.2 Data Monitoring Committee (DMC), Data Review Team (DRT) or Dose Level Review Team (DLRT)

Dose Level Review Meetings (DLRMs) will be held to review data, monitor safety, and make decisions on dose escalation / change. The DLRT will be composed of the investigators or designees, and the following Amgen representatives: medical monitor, global safety officer or designee, clinical study manager, biostatistician, additional members may be added as needed (eg, clinical pharmacologist). The following members are responsible for DLRT decisions: investigators, Amgen medical monitor, and global safety officer or designee. All available study data, including data collected after the initial DLT window, and including demographics, IP administration, medical history, concomitant medications, adverse events, ECGs, vital signs, laboratory data, and PK/PD information will be reviewed. In addition to DLTs, all \geq grade 3 toxicities not meeting DLT criteria will be reviewed and may be considered in DLRT decisions. Modeling of available potential safety risk data (eg, for thrombocytopenia) to predict safety risk for dose escalation decisions may also be considered.

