10.4.2.3 Dose Limiting Toxicities

The analysis of the probability of dose limiting toxicities (DLT) will include data from DLT-evaluable subjects, both from dose-exploration and dose-expansion (see [section 3.4](#) for definition of DLT-evaluable). The primary analysis will only include DLTs that occur within the protocol defined DLT evaluation interval. If DLTs occur outside the specified evaluation interval, a sensitivity analysis will be performed where DLTs occurring outside of the specified time interval are included. The preliminary estimate of the MTD will be identified using the 3+3 design. A final estimate of the MTD will be made based on a toxicity probability interval (TPI) Bayesian model utilizing all DLT evaluable subjects from the dose exploration and dose expansion cohorts ([Babb, 1998](#)). A minimally informative prior distribution will be used for the model parameters ([Neuenschwander, 2008](#)). The MTD target probability interval is (0.20, 0.35) and TPIs of (0.35, 0.60) and (0.60, 1.00) are defined as excessive and unacceptable, respectively. The model's predicted MTD is the dose with the highest probability of the target TPI, but with a less than 0.25 probability of an excessive or unacceptable TPI.

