3.1 Study Design

This is a Phase 1, first-in-human, multicenter; non-randomized, open-label, dose-exploration and dose expansion study of AMG 224 IV Q3W for subjects with relapsed or refractory multiple myeloma. The study will be conducted in two parts:

Part 1- Dose Exploration to define the MTD and / or RP2D followed by **Part 2 - Dose Expansion** to obtain further safety and efficacy data.

Eligible subjects enrolled in the study will receive AMG 224 IV once Q3W beginning at study Day 1. During the initial DLT window (Day 1 through Day 28) subjects will be assessed for DLT. DLTs are defined in protocol Section 6.2.1.6. Dosing with AMG 224 may continue Q3W unless there is evidence of progressive disease (PD) defined by IMWG, the subject becomes intolerant to the study medication, signs and symptoms of clinical progression are evident as determined by the principal investigator, or the subject withdraws consent.

Part 1 – Dose Exploration

In Part 1 for the first dose level and at each new higher dose level, the first enrolled subject will be treated, and then after a period of 24 hours, subsequent subjects will be treated, provided that there are no safety concerns relating to the treatment of the first subject.

The dose-exploration cohorts will define the preliminary MTD, safety, tolerability, PK, and PD of AMG 224. A 3+3 design will be used to make a preliminary estimate of MTD. The preliminary MTD is defined as the maximum dose at which fewer than **33% of subjects** experience a DLT. A final estimate of the MTD will be made using data from Dose Exploration and Dose Expansion. Planned dose levels for the dose-exploration cohorts are as follows: 30, [REDACTED] of AMG 224 (IV; Q3W).

Dose exploration decisions will be made by the Dose Level Review Team (DLRT). All cumulative safety and laboratory data will be reviewed prior to making dose exploration decisions. Safety data from all enrolled subjects in preceding cohorts and dose levels will also be considered. Additionally, the DLRT may stop enrolment into a cohort at any time to evaluate safety.

3+3 Design:

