7.1 Interim Analysis and Early Stopping Guidelines

Safety data will be reviewed on an ongoing basis. **The Dose Level Review Team (DLRT, see protocol Section 10.3.2) will review all available cumulative data by cohort prior to making dose escalation decisions. Adverse events and DLTs observed in all subjects will be evaluated continually and considered in all enrollment and dosing decisions.**

During dose-expansion, the DLRT will review safety after 5 subjects have enrolled (combining Group A and Group B subjects) and completed 28 days on study. A TPI Bayesian model (see protocol Section 10.4.2.3) utilizing all current DLT-evaluable subjects will be fit to evaluate the appropriateness of the preliminary MTD from dose exploration. The subsequent subjects to be enrolled in dose expansion may be dosed with the updated dose level, determined by the DLRT.

Early stopping guidelines will be implemented as explained in the protocol Sections 6.2.1.2-1.4.

7.2 Data Monitoring Committee (DMC), Data Review Team (DRT) or Dose Level Review Team (DLRT)

Dose Level Review Meetings (DLRMs) will be held to review data, monitor safety, and make decisions on dose escalation / change. The DLRT will be composed of the investigators or designees, and the following Amgen representatives: medical monitor, global safety officer or designee, clinical study manager, biostatistician, additional members may be added as needed. The following members are responsible for DLRT decisions: investigators, Amgen medical monitor, and global safety officer or designee. All available study data, including data collected after the initial DLT window, and including demographics, IP administration, medical history, concomitant medications, adverse events, ECGs, vital signs, laboratory data, and PK/PD information will be reviewed. In addition to DLTs, all \geq grade 3 toxicities not meeting DLT criteria will be reviewed and may be considered in DLRT decisions. Modeling of available potential safety risk data (eg, for thrombocytopenia) to predict safety risk for dose escalation decisions may also be considered.

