9.6.1.2 Dose Limiting Toxicities

The analysis of the probability of DLT will be based on the DLT Evaluable Analysis Set. A listing and summary of the subject incidence of DLT will be provided.

A final estimate of the MTD will be estimated from the TPI Bayesian model utilizing all DLT-evaluable subjects. A sensitivity analysis may also be performed where DLTs

occurring outside of the specified time interval are included. A listing of DLTs occurring outside of the specified time interval will be produced to aid in determining if the sensitivity analysis should be conducted.

The planned doses for dose exploration cohort are 30, [REDACTED] of AMG 224. It will use a standard 3+3 design to guide dose escalation decisions and to make a preliminary estimate of the MTD. Dose level decision rules are specified in [Table 1](#).

In the dose expansion cohort, up to 20 subjects would be treated at the preliminary MTD. After 5 subjects (combining Group A and B) have completed 28 days on study, there will be a safety review by the DLRT. A TPI Bayesian model utilizing all current DLT evaluable subjects will be fit to evaluate appropriateness of preliminary MTD from dose exploration phase. As more subjects are treated, there may be a higher than expected incidence of DLTs or a higher than expected tolerance of treatment. If these scenarios (either with higher toxicity or tolerance) occur during expansion cohort the additional data will be used to refine the estimate of MTD established during the dose escalation phase. (Iasonos A and O'Quigley J, 2013).

A minimally informative prior distribution will be used for the model parameters (Neuenschwander, 2008). The MTD target probability interval is (0.20, 0.35) and TPIs of (0.35, 0.60) and (0.60, 1.00) are defined as excessive and unacceptable, respectively. The model's predicted MTD dose is the dose with the highest probability of the target TPI, but with a less than 0.25 probability of an excessive or unacceptable TPI.

The TPI design seeks to identify a dose most likely to have a DLT rate in the target TPI, but with overdose control that limits the possibility that the dose has an excessive or unacceptable DLT rate ([Babb et al, 1998](#)). The probability of a DLT at dose level d_i is assumed to follow a Bernoulli distribution with probability p_i where the logit of p_i increases linearly with the log of the standardized dose in the following 2-parameter logistic model:

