5. Vital signs
6. Reported adverse events (AEs)
7. Safety laboratory data (chemistry, hematology, urinalysis, coagulation)
8. Current malignancy
9. Medical history
10. Concomitant medications
11. Prior anti-cancer therapy and prior radiotherapy data
- 12. Quantification of Immunoglobulins**
- 13. SPEP**

Figures

1. Line plot of vital signs by time course
2. Line plot of all safety labs by time course
3. Line plot of ECGs results by time course
4. Plot of the posterior probability of DLT (Expansion phase)
5. Distribution plot of the predicted MTD (Expansion phase)
6. Bar chart of the number of subjects studied per dose in dose exploration phase
7. **Protein_M1 line plot**

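### The DLT definition is limited to Part 1, yet the interim and final TPI models need DLT outcomes from Part 2 subjects, and no Part 2 definition exists

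*Protocol*

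**What the plan says.** Protocol 6.2.1.6 opens its definition with a grade threshold and a day 1–28 window, and confines the event to one part of the study: "in Part 1 Dose Exploration unless clearly attributable to causes other than AMG 224 treatment". SAP Section 5 (Definitions, Dose Limiting Toxicity) carries the same limit. Only the Hy's Law sentence in each document is written for any subject.

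The analysis text covers both parts. Protocol 10.4.2.3 says that the analysis of the DLT probability "will include data from DLT-evaluable subjects, both from dose-exploration and dose-expansion". For the interim look after 5 expansion subjects have completed 28 days, SAP 7.1 says: "A TPI Bayesian model (see protocol Section 10.4.2.3) utilizing all current DLT-evaluable subjects will be fit to evaluate the appropriateness". Protocol 10.3.1 then says: "The subsequent subjects to be enrolled in dose expansion may be dosed with the updated dose level, determined by the DLRT". SAP 9.6.1.2 explains the purpose of the expansion data: "As more subjects are treated, there may be a higher than expected incidence of DLTs or a higher than expected tolerance of treatment".

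Protocol 3.4 and SAP 6.3 say who is DLT-evaluable. A subject is excluded if treatment stops before day 28 for any reason other than a DLT, or if two doses are not received in the 28-day window. The second condition has no exception for a DLT.

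**The concern.** Both model fits need a yes/no DLT status for every evaluable Part 2 subject, and the only definition available excludes Part 2. Followed literally, a Part 2 subject with a qualifying event is scored as DLT-free unless it is a Hy's Law case. If treatment stops early because of that event, the subject has stopped for a reason other than a DLT and leaves the analysis set. Either way the estimated DLT rate at the expansion dose falls. The excess toxicity that SAP 9.6.1.2 expects the expansion cohort to reveal would then largely fail to reach the model. The MTD is a primary objective and DLT incidence a primary endpoint.

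The two-dose rule is a separate route to the same bias and does not depend on the Part 1 phrase. Protocol 6.2.1.5 withholds drug for a suspected DLT, so a first-cycle DLT in either part can prevent the second dose and remove the subject.

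**Working it through.** **Is there a Part 2 definition anywhere?**

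- Protocol 6.2.1.3 (dose expansion) describes a safety review and defines no DLT.
- Protocol 6.2.1.2 restates the DLT concept without the Part 1 words, but it is in the exploration section and refers to 6.2.1.6.
- Protocol 3.1 says of all enrolled subjects: "During the initial DLT window (Day 1 through Day 28) subjects will be assessed for DLT". It and SAP 3.1 also refer to 6.2.1.6.
- Protocol 3.4 and SAP 6.3 define evaluability, not the event.

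These passages show intent but supply no definition.

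**The plan's own figures.** The DLT sample-size figures in Protocol 10.2 reproduce: 1 − 0.9³ = 0.271 and 1 − 0.67³ = 0.699 for 3 subjects; 1 − 0.9⁶ = 0.469 and 1 − 0.67⁶ = 0.910 for 6. They are not in dispute. The plan gives no figure for the point at issue, so what follows is an illustration.

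**Inputs from SAP 9.6.1.2 and Appendix A.**

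- Model: logit p = log α + β·log(d/d_max).
- Prior: bivariate normal for (log α, log β), means 0.0536 and −0.1469, SDs 1.685 and 1.001, correlation −0.216.
- Selection rule: the dose with the largest P(0.20 < p < 0.35) among doses with P(p > 0.35) < 0.25.

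**Assumptions.** d_max = 300 mg (from the 30 to 300 mg range in Protocol 6.2.1.1) and a ladder of 30/45/70/105/150/190/250/300 mg. The weight-based Part 2 dose is treated as a single fixed dose. The posterior was integrated on a grid.

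**Case (a).** Part 1 cohorts of 3, 3, 3, 3, 3, 3, 6, 3 with 1/6 DLTs at 250, 2/3 at 300 and none below. Expansion at 250.

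| Expansion DLTs counted | Mean rate at 250 | P(p > 0.35) at 250 | P(p > 0.35) at 300 | Dose selected |
|---|---|---|---|---|
| 8/20 | 0.32 | 0.35 | 0.83 | 190 |
| 4/20 | 0.21 | 0.03 | 0.43 | 250 |
| 0/20 | 0.09 | 0.000 | 0.18 | 300 |
| 3/5 (interim) | 0.31 | 0.35 | 0.76 | 190 |
| 0/5 (interim) | 0.16 | 0.02 | 0.32 | 250 |

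Selection stays at 250 for 5, 6 and 7 of 20 and first drops to 190 at 8 of 20. At 1/20 the selected dose is 300, as at 0/20.

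If subjects with events are dropped instead of kept as DLT-free, 8/20 becomes 0/12 (mean 0.12) and 3/5 becomes 0/2 (mean 0.19). The selected doses are the same as for 0/20 and 0/5.

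**Case (b).** No DLTs in Part 1, 3 subjects at each lower dose and 6 at 300, expansion at 300. Protocol 6.2.1.2 allows the maximum administered dose to be carried forward in this situation.

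| Expansion DLTs counted | Mean rate at 300 | P(p > 0.35) at 300 | Dose selected |
|---|---|---|---|
| 9/20 | 0.31 | 0.28–0.29 | 250 |
| 8/20 | 0.27 | 0.16–0.17 | 300 |
| 4/20 | 0.15 | 0.004 | 300 |
| 0/20 | 0.04 | 0.00 | 300 |

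At an interim 3/5, P(p > 0.35) is 0.10–0.11 and 300 is kept. The ranges reflect the integration grid.

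**Simpler assumed Part 1.** With 0/3 at 30 mg, 0/3 at a middle dose and 1/6 at an expansion dose of 150, 200 or 250 mg, an interim 3/5 gives P(p > 0.35) of 0.285 to 0.374 if counted and 0.007 to 0.015 if scored 0/5. That crosses the 0.25 limit.

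**How likely are such counts?** From the binomial with n = 20, P(at least 8) is 0.23 at a true rate of 0.30 and 0.58 at 0.40. P(at least 9) is 0.11 and 0.40.

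**The case against.** The strongest reply is that this is one leftover phrase and the intent is plain. Protocol 10.4.2.3 names both parts. Protocol 3.1 has all enrolled subjects assessed for DLT. Protocol 6.2.1.5 ties events meeting the DLT definition to Table 3, which applies only in expansion, and speaks of the time after the DLT window in that part. SAP Appendix A plans an expansion-phase plot of the posterior DLT probability. Scoring Part 2 as toxicity-free would defeat all of this. That stands: the point is a contradiction to reconcile, not evidence of a plan to ignore Part 2 toxicity.

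It is also true that practical harm is limited. The DLRT sees all safety data, including grade 3 or higher events that are not DLTs. It determines interim dose changes and the RP2D, and Part 2 adverse events are tabulated whatever their label. This protects subjects and dosing decisions, but it does not correct the binary input to the reported model-based MTD.

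The illustration needs high counts (8 or 9 of 20) before the model steps down, and it rests on assumed doses and data. Scoring every event as DLT-free is the extreme case, but dropping those subjects gives the same direction and the same selected doses.

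The two-dose rule is a separate issue. The replacement rule in Protocol 6.2.1.2 suggests that subjects with a DLT are meant to be kept, but the two-dose condition itself is unqualified.

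**Conclusion.** The concern holds and should be fixed. Both documents restrict a DLT to Part 1, both TPI fits draw on Part 2, and nothing else defines a Part 2 DLT. If the listed criteria are applied in Part 2, as other text implies, the phrase causes no bias. If the wording is followed, the DLT rate at the expansion dose is biased downward apart from Hy's Law cases.

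The size is illustrative only. With 8 of 20 events, the mean rate falls from 0.32 to 0.09 in case (a) and from 0.27 to 0.04 in case (b). The selected dose changes in case (a) and not in case (b), so an effect on the MTD depends on the Part 1 outcome and the event count. These figures rest on an assumed ladder, d_max, Part 1 results and a fixed Part 2 dose, because the real doses are redacted. The textual contradiction and the direction of the bias do not depend on those assumptions.

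**What to change.** In Protocol 6.2.1.6 and SAP Section 5, state that for the DLT analysis and the TPI models the day 1–28 DLT criteria apply to subjects in both parts, as Protocol 10.4.2.3 already assumes. In Protocol 3.4 and SAP 6.3, state that for this analysis a subject in either part who stops early, or misses the second dose, because of an event meeting those criteria is evaluable and counted as having a DLT.

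The cost is two sentences in each document. Adverse event, laboratory and dosing data are already collected in Part 2, so no new assessments are needed. The withholding and discontinuation rules in Protocol 6.2.1.5 also use the term DLT. The sponsor should check those rules against the revised scope and reconcile any effect on them; this change concerns the analysis only.
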